5.6 Identification of the subject

Study subjects will be identified by a number and the initials of their name.

The initials of the study subject will be obtained starting with the first letter of the name, followed by the first letter of the first surname and the first letter of the second surname, obtaining a maximum of three letters, in case the person has two names or compound surname, the first letter will always be used.

Example:

To. [name]

to. Initials: AMC

B. [name]

[figure not shown]
b. Initials: JDO

In the counting stage, the participant number will be assigned consecutively, using 3 consecutive digits.

Once the subject has been selected, they will be assigned a number with which they will be identified throughout the study. This code will be made up of eight numbers in the following order from left to right:

- three digits of the molecule under study according to the name by the sponsor.
- Two digits corresponding to the research centre number.
- three digits of the number following their inclusion assigned in the research centre.

Example of assigned number:

6. Investigational product and treatment

6.1 Interventions

6.1.1 Investigational product

- PRO- 23 1 . Moxifloxacin 0.5% Ophthalmic solution . . Zapopan, Jalisco, Mexico.
Laboratorios Sophia, S.A. de C. V
- Route of administration: Ophthalmic.
- Pharmaceutical form: Ophthalmic solution.
- Presentation: multi-dose dropper bottle, 5 mL.
- Prepared by: Laboratorios Sophia, S.A. de C.V.

- Solution description: transparent, free of visible particles and yellow in color.
- Packaging description: White bottle made of low-density polyethylene filled to 5 mL.

6.1.2 Investigational Product Dosage

Dosage: 1 drop three times a day (DID) for 7 days, in the right eye (OD).

6.1.3 Treatment with the investigational product

The product under investigation will be delivered at the conclusion of the baseline visit. The subject under investigation will begin the application the next day (day 1) by administering one drop every 6 hours, applying a total of one drop three times a day to the right eye during the 7 days of application.

6.1.4 Comparison Product

- VIGAMOXI® Moxifloxacin 0.5% Ophthalmic solution . Alcon Laboratories, Inc. Fort Worth, Texas, USA.
- Route of administration: Ophthalmic.
- Pharmaceutical form: Ophthalmic solution.
- Presentation: multi-dose dropper bottle, 5 mL.
- Prepared by: Alcon Laboratories, Inc.
- Description of the solution: transparent, greenish-yellow solution.
- Packaging description: Natural low-density polyethylene bottle and a dosing cap with polypropylene closure (Drop-trainer® dispensing system) filled to 5 mL.

6.1.5 Comparator Product Dosage

Dosage: 1 drop TID for 7 days, in OD.

6.1.6 Treatment with the comparator product

The product under investigation will be delivered at the conclusion of the baseline visit. The subject under investigation will begin the application the next day (day 1) by administering one drop every 6 hours, applying a total of one drop three times a day to the right eye during the 7 days of application.

6.2 Storage and handling of the investigational product in the study center

The delivery will be made by means of a courier service contracted by the sponsor, expressly selected for this purpose, to the address of the research center according to the study plan.

The reception will be carried out by the assigned personnel of the research team. You will need to check that the primary packaging (box) is in good condition. In the event that you show alterations or defects in its integrity that in your judgment could have damaged the content, you must report it to the sponsor. If the package does not show significant defects, it will proceed to open it.

Inside the shipment you must locate the acknowledgment document and the temperature meter (*data logger*). You must check that the temperature recorded complies with what is specified for transport and safekeeping. It will verify the content (PI) with what is reported in the document. In case the document corresponds to the content, you will sign the receipt and send it to the sponsor. Otherwise, it will notify the sponsor.

Storage and safeguarding is the responsibility of the research center. The medication must be stored in a secure area with restricted access.

The storage temperature should be 2° to 25°C.

From its receipt at the center and until there is no stock of PI stored, the research center has the obligation to review the storage conditions of the PI on a daily basis and manually record, in the designated format, the temperature set by the *data logger* (current, minimum and maximum temperature). Such data will be reviewed by the clinical monitor during their monitoring visits according to the records stored in the *data logger's memory*.

In the event of loss of material, it must be documented in the logbook of inputs and outputs along with a clear description of the mechanism by which the loss occurred.

Upon completion of the protocol, all study material will be retrieved by the sponsor as part of the closing visit. The final delivery of material will be made by the principal investigator or the person designated by him to deliver material at the end of the study.

The sponsor reserves the right to initiate civil and criminal action against the principal investigator in the event of a lack of undocumented material at the conclusion of the study.

6.3 Concomitant treatments and medications (permitted and prohibited)

Any medication that is used, in addition to appearing in the clinical note, must be registered in the concomitant medication section of the eCRF (*electronic Case Report Form*).

6.3.1 Permitted Medications

- Ophthalmic:

All permitted medications applied via ophthalmic medication during the study must wait a minimum period of 10 minutes from the last application of the treatments under study or reference. The above in order to avoid the interaction of treatments in the tear film, based on the flow index and physiological tear volume. [22]

- Tetracaína 0.5%
- Tropicamida 0.8% /Phenylephrine 5%
- Hipromelosa 2%
- Fluorescein

- Systemic:

In case participants of childbearing potential decide to use a hormonal contraceptive method, the following will be allowed:

- o Oral contraceptives.
- o Subdermal implant.
- o Parenteral injection.
- o HORMONAL DIU.

6.3.2 Prohibited medicines:

- Any ophthalmic or systemic medications that are not on the list of allowed medications.

6.4 Procedure for monitoring and measuring adherence

For more than four decades, numerous investigations have been conducted on the appropriate way to measure and quantify medication adherence, however, none has reached a consensus to stand as the gold standard, both in cross-sectional and longitudinal studies. [23, 24, 25, 26, 27, 28, 29, 30]

There are different procedures to measure adherence to pharmacological interventions. The most common procedure includes self-reports, which include: interviews with the subject, questionnaires and self-monitoring diaries. Its strengths are speed, flexibility, low cost and ease of implementation; They have a high degree of specificity for non-adherence, however, the sensitivity and reliability for adherence is low. [30, 31]

The biochemical measurement of the drug, or its metabolite, is one of the methods that best confirms the use of the drug. However, in addition to raising costs and being impractical, it is of little use in the context of ophthalmic applications, since concentrations at the peripheral level could be undetectable; and samples of other tissues involve more invasive methods that would not be advisable. [30]

There is no standardized parameter to define adequate adherence, it must be defined and delineated by the objectives of the particular research. [30]

For this study, a minimum adherence of 80% (per subject's diary) will be considered to be necessary to meet the objectives of the research; In turn, the information in the diary will be corroborated with the final weight of the research product with respect to its initial weight. Therefore, subjects with adherence of less than 80% will not be considered for the study.

6.5 Strategies to improve adherence

1. The PI will sensitize the subject to the importance, in order to achieve the objectives of the study, of the correct application of the concomitant treatment.
2. Direct questioning by the PI about the application of the concomitant treatment.
3. Delivery of a printed calendar specifying the date of the visit and its activities.

If deemed necessary, text messages may be sent as reminders. The content of these messages must be previously approved by the Research Ethics Committee (ERC).

7. Study methods and procedures

7.1 Research centre

This study will be carried out in a research center previously evaluated by the sponsor. The center will be an institution or establishment where health research is carried out that complies with current regulations.

The research center will be responsible for forming a multidisciplinary research team to execute the clinical study according to the protocol. It is their prerogative to design the organization and select the personnel who will perform the functions. However, it is necessary for the sponsor that the PI and sub-investigator be ophthalmology specialists.

Any person who is designated, under the responsibility of the PI, a part of the study monitoring (sub-investigator, nurse, etc.) or a specific function of participation in the study (pharmacist, administrative assistant, study coordinator, etc.) must appear in the "Delegation of Responsibilities".

The competence and training of any person who has direct participation in the activities of the study must be verified prior to the performance of any activity related to the protocol. The above must be recorded and the documents that constitute evidence of this competence and/or training must be kept in the master file of the study. The competence and training of the personnel who have functions in the study, both at the central level and in the study center, is the responsibility of the principal investigator. [32]

The sponsor must ensure that all study site personnel participating in the study are adequately trained on the study (research protocol, investigator's manual, amendments, standard operating procedures, etc.) and on the Good Clinical Practices of the ICH (International Council on Harmonization) *International Council for Harmonisation*), before the start of their participation in it. Training must be recorded in writing and those records must be filed in the master record of the study. [32]

7.2 Clinical Study Registration

This clinical study will be registered by the sponsor in public clinical trial registries before its start (inclusion of the first subject): National Registry of Clinical Trials (RNEC) of the Federal Commission for the Protection against Sanitary Risks (COFEPRIS) and in a primary registry platform of the World Health Organization (WHO). WHO primary registries meet specific criteria for content, quality and validity, accessibility, unique identification, technical capacity, and administration. WHO Primary Registries meet the requirements of the International Committee of Medical Journal Editors (ICMJE).

7.3 Assignment of treatment

The assignment/randomization of the treatment will be carried out centrally using a validated electronic system from an external provider, previously evaluated and authorized by Laboratorios Sophia S.A. de C.V. There are two treatment groups. Participants will be randomized in a 1:1 ratio to treatment with PRO-231 or VIGAMOXI.® Having the same probability of being assigned to one or the other treatment. After signing the FCI, the subject will receive a participant number with which all their information will be encrypted pseudonymity during collection and completely anonymized during analysis. The generation will be carried out by a third party, authorized by Laboratorios Sophia, S.A. de C.V., through its electronic system, through a list of random numbers generated by software (SAS Institute Inc, Cary, NC, USA). The information pertaining to this third party will be on file. Only the principal investigator and the person responsible for the statistical analysis will be blinded, because the primary packaging of the comparator cannot be modified to resemble the product under investigation. Despite this, the secondary packaging for the products will be the same and the researcher will not know the allocation. IP will be identified by means of labels in accordance with current and applicable regulations, which must contain at least:

- Sponsor's name, address, and phone number.
- Dosage form and route of administration.
- Number of doses.
- Batch number.
- Legend "Exclusively for clinical studies".
- Expiration date.

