4.2 Rationale for the study design

The design of the study (clinical trial) is considered the highest standard of data quality when seeking to explore the effect of an intervention. The drug development phase (phase I) corresponds to the objective of the study, which is to evaluate safety and tolerability, so the intervention time is short and the sample size required is smaller than that of an efficacy clinical trial.

Although this is a comparative study with two intervention groups, only the principal investigator and the person responsible for the statistical analysis will be blinded, because the primary packaging of the comparator cannot be modified to resemble the product under investigation. Despite this, the secondary packaging for the products will be the same and the researcher will not know the allocation.

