7.4.4.2 Chemosis

It is defined as conjunctival edema, the result of an inflammatory reaction. It is qualified as present or absent. The evaluator will use a narrow beam of light at 60° and will measure whether the conjunctiva separates from the sclera by $\geq 1/3$ of the total eyelid opening or if it exceeds the gray line. [39]

The PI will record in the file and the eCRF if the chemosis is absent or present.

Management as AE: An adverse event will be considered when present.

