7.4.4.7 Eye Comfort Index

It is a questionnaire designed to measure ocular surface irritation with Rasch analysis to produce estimates on a linear interval scale (ratings: 0-100). Similar to the index for ocular surface diseases, the ocular comfort index (ICO) assesses symptoms. The ICO contains 8 items (one positive and eight negative) that focus on discomfort associated with ocular surface alterations. Each of these questions has two parts, which separately inquire about the frequency and severity of symptoms. [\[43\]](#) See attachment [16.4 Eye Comfort Index \(JI\)](#)

At the baseline visit and final visit, the evaluator will deliver the questionnaire to the subject and allow the subject to answer it calmly without any pressure and/or coercion, only assisting him if he has difficulty understanding any of the questions.

As it is a subjective measurement scale according to the subject's symptomatology, variations in the ICO cannot be managed as AEs.

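### Blinding covers only the PI and the statistician, so the plan allows unmasked staff to take subjective primary measurements, and the PI could see the returned bottle before day-8 grading

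*Combined protocol and SAP*

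**What the plan says.** **Who is blinded.** Section 7.3 states "Only the principal investigator and the person responsible for the statistical analysis will be blinded", and Section 4.2 has the same rule: "only the principal investigator and the person responsible for the statistical analysis will be blinded". The reason given is that the comparator's bottle cannot be made to look like the test product's. The safeguard offered is that "the secondary packaging for the products will be the same and the researcher will not know the allocation".

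**What the bottles look like.** The test product (Section 6.1.1) comes in a "White bottle made of low-density polyethylene filled to 5 mL". The comparator (Section 6.1.4) comes in a "Natural low-density polyethylene bottle and a dosing cap with polypropylene closure".

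**Who works at the site.** Section 7.1 leaves staffing and the division of tasks to the centre, with delegated roles to be logged. It adds that "it is necessary for the sponsor that the PI and sub-investigator be ophthalmology specialists". Nothing is said about masking the sub-investigator.

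**Who measures.** For chemosis, Section 7.4.4.2 says "The evaluator will use a narrow beam of light at 60" degrees, and the PI then records the result. In Section 7.4.4.4 the evaluator points out and notes the acuity line. In Section 7.4.4.7 "the evaluator will deliver the questionnaire to the subject" and may help if a question is not understood. Sections 7.4.4.1 (hyperemia) and 7.4.4.5 (staining) have the PI record the grade without saying who assigns it.

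**When the product comes back.** Section 7.7.3 lists product return at the final visit, alongside the day-8 examinations and the ICO. Section 7.7 lets the investigator choose the order of procedures.

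**The concern.** The Efron grade, the presence of chemosis, the match to an Oxford panel and the accepted acuity line all involve observer judgement. Several also feed cut-offs that define an adverse event (hyperemia grade 3 or more, any chemosis, staining grade III or more, loss of two lines), so a one-step shift at a cut-off can create or remove an event.

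Subjects are not blinded, so a masked examiner is the main protection these endpoints have against detection bias. If the examiner may be someone outside the blind, or may see the bottle first, that protection is not secured. Section 10.3.1 reads a non-significant result whose confidence interval includes zero as similarity. An examiner who expects no difference could push towards that reading, and one with the opposite expectation could push away from it.

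**Working it through.** The blinding rule has no figure to reproduce, so the main check sets the rule against each primary variable in Section 7.4.1 (hyperemia and chemosis shown separately).

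| Primary variable | Who measures or judges | Who records | Tied to a blinded person? |
|---|---|---|---|
| Unexpected related AEs (Table 2, 8.5.4) | PI judges causality at the site | PI | Yes |
| Hyperemia (7.4.4.1) | Not named | PI | Recording only |
| Chemosis (7.4.4.2) | Evaluator | PI | Recording only |
| BCVA (7.4.4.4) | Evaluator | Evaluator notes the line | No |
| Staining (7.4.4.5) | Not named | PI | Recording only |
| ICO (7.4.4.7) | Subject answers; evaluator hands out and may assist | Not named | No |

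Only the first row assigns the judgement itself to a blinded person. Because Sections 4.2 and 7.3 use the word only, an evaluator or sub-investigator who is not the PI falls outside the blind. No section masks these people or reserves the primary assessments for masked staff. A site could follow the protocol exactly and still have an unmasked person measure.

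There are two routes of exposure:

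1. **Unmasked assessor, days 3 and 8.** This applies whenever someone other than the PI measures.
2. **Sight of the bottle, day 8.** The timetable places product return only at the final visit. Someone must also handle the bottle, because Sections 5.2.1, 6.4 and 10.3.2.1 use its weight to corroborate adherence. Nothing separates that person from the examiner or puts the return after grading. This route can reach the masked PI as well.

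**Upper bounds.** Section 10.1.2 raises 17 per arm by 10%: 17 × 1.10 = 18.7 and 17 / 0.90 = 18.9, both rounding up to 19, and 2 × 19 = 38. Ignoring replacements, route 1 can touch at most 38 × 2 = 76 examinations, and only if the PI examines nobody after dosing. Route 2 can touch at most 38 × 1 = 38.

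**Sensitivity to re-grading.** If all 19 per arm are analysed, two re-graded subjects move an arm's incidence by 2/19 = 10.5 percentage points. Starting from zero events in both arms, two-sided Fisher tests give:

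- 0/19 v 2/19: p = 2 × C(19,2)/C(38,2) = 2 × 171/703 = 0.49
- 0/19 v 4/19: p = 2 × 3,876/73,815 = 0.105
- 0/19 v 5/19: p = 2 × 11,628/501,942 = 0.046

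From that starting point, two re-grades would change the reported incidence but not the test result; five would be needed. None of these figures estimates bias.

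**The case against.** The strongest reply is that the evaluator is simply the PI. The PI records hyperemia, chemosis and staining, records adverse events, and under Section 8.5.4 is responsible for examining the subject and judging causality. The translated text moves freely between PI, investigator, researcher and evaluator, and the statement that the researcher will not know the allocation suggests the examining doctor was meant to be masked. This stands in part: the PI may well do much of the grading. It does not close the gap. The researcher clause directly follows the restrictive sentence and names no other examiner, while Section 7.1 plainly expects a second ophthalmologist.

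A reader might go further and infer more than the documents support:

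- **That unmasked grading is planned, or that 76 examinations will be unmasked.** No section says an unmasked person will grade, or that the sub-investigator is told the allocation.
- **That every subject knows the product.** Subjects are not blinded, but each receives one bottle in a matching outer pack, and the minimum label content in Section 7.3 lists no product name. Not being blinded is not the same as knowing the arm.
- **That symptom questioning is an exposed primary measure.** Section 7.4.2.2 makes it secondary.
- **That masking the evaluator would protect the ICO.** The subject answers it, so most of any bias there would remain.

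It is also fair to say that the protocol openly declares a single-blind design and explains the packaging constraint. That explains why the bottles differ. It does not explain why the blind stops at the PI, or why the bottle may reappear before the examination.

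**Conclusion.** The concern holds as a gap in the masking rule. As written, the plan allows subjective primary measurements to be taken by an unmasked person at days 3 and 8, and allows even the masked PI to see the bottle before the day-8 grading. The gap is most explicit for chemosis and BCVA, where the evaluator measures. It is less direct for hyperemia and staining, where only the recorder is named.

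Its size cannot be derived from the documents: 76 and 38 examinations are ceilings, and the 10.5-point figure is only a sensitivity. The direction of any bias is unknown. The conclusion rests on reading the word only in Sections 4.2 and 7.3 literally and on the absence of any definition of the evaluator. If the sponsor always meant the PI to make every assessment, saying so would close the first route but not the second. The change is worth making before enrolment because it alters conduct at very little cost.

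**What to change.** 1. **Extend the blind in Sections 4.2 and 7.3.** State that anyone who grades hyperemia, chemosis, staining or BCVA, administers the ICO or judges AE causality is blinded to allocation. Alternatively, state that the blinded PI performs all of these. Define the evaluator accordingly in Section 7.4.4.
2. **Separate product handling from assessment.** Assign product delivery, bottle return and weighing to an existing team member who makes no assessments, and record this in the delegation log. Section 7.1 already mentions a nurse, pharmacist and study coordinator.
3. **Fix the order at the final visit.** In Section 7.7.3, have the bottle returned in its identical outer carton, to that team member, after the day-8 examination is recorded.

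The cost is a few sentences and a delegation-log entry; sample size and visits do not change. The small downside is that the person handling the product cannot act as evaluator. The change protects the examination-based primary variables. It does not remove bias in ICO answers from subjects who are not masked, and the report should state that limit.
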